If subjects successfully complete the vibration screening they will continue with the following assessments during Visit 1:

General Health and Function: The 36-Item Short Form Health Survey Walk Wheel (SF-36 WW) is a slightly modified version of the original SF-36 that has been validated for persons with SCI. The SF-36 is a brief, multi-dimensional, self-report health questionnaire that measures eight concepts - Physical Functioning,

Role limitation due to Physical problems, Bodily Pain, General Perception of Health, Vitality, Social Function, Role limitation due to Emotional problems, and Mental Health. The domain scales ranges from 0 (worst possible health state measured by the questionnaire) to 100 (best possible health state).

Power output: the Lode Arm Ergometer will be used to measure the maximum power output for each participant. This test will be done with the participant seated in their wheelchair. The arm ergometer height will be adjusted such that participants are able to comfortably reach and crank both pedals. Additionally, we will want subjects to be in a stable participation. If they are able to, participants should brace their feet on their foot plate. If a participant does not feel enough stability in their wheelchair we will have a stable chair for them to transfer to in order to perform the evaluation. Participants will start out by cycling on the arm ergometer at a comfortable pace as a warm up. Once the participant feels as though they are sufficiently warmed up the test will begin. Participants will begin cycling against maximum resistance. Once that happens participants will be instructed to cycle as hard and as fast as they can for as long as they are able to. Once they are no longer able to crank against the resistance the test will stop and the maximum resistance will be recorded. We will complete this process three separate times, with a minimum of 30 seconds of rest in between. After the test is completed, the resistance will return to zero and the participants will cycle at a comfortable pace to cool down. They will cycle as long as they need to in both the warm up and cool down phases.

Muscle Strength Testing

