Isokinetic strength measurements will be recorded at a torque arm speed of 60 deg/sec using an instrumented dynamometer (BiodeX Medical System, New York, USA). The torque measurements will be recorded in a randomized fashion for both arms for the following test maneuvers: shoulder flexion/extension in the sagittal plane (-30 to 50 degrees), shoulder abduction/adduction in the frontal plane (10 to 70 degrees), shoulder internal/external rotation in the transverse plane (0 to 45 degrees), elbow flexion/extension (0 to 90 degrees), forearm supination/pronation (-80 to 80 degrees) and wrist flexion/extension (-45 to 45 degrees) and grip strength. One trial of 5 practice repetitions for each movement tested will be completed prior to data collection. In order to ensure the maximal force production of the tested upper extremity subjects will be secured into the chair with three padded belts: two diagonally across their chest and one across their lap. After the practice trial, one trial of five repetitions will be recorded for each muscle group. In between the practice trial and data collection trial, participants will rest a minimum of 60 seconds and in between each muscle groups participants will rest a minimum of 2 minutes. Participants may request additional time as needed. After completing all the strength testing subjects may rest before performing the functional tests.

Functional Testing

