Training intensity will be adjusted progressively with add-on dumbbell weights that will be added to the vibrating dumbbell. Subjects will be asked to hold onto the vibrating dumbbell tightly for as long as they can for each exercise. If they are unable to hold on tightly for at least 15 seconds, the weight for the next session will be decreased, whereas if they are able to hold onto the dumbbell for greater than 60 seconds, the trainer will stop the exercise and the dumbbell weight will be increased for the next session. The amount of weight increased and decreased will be determined by the trainer and will be reviewed and verified by a member of the senior study personnel.

The trainer will meet with the senior study personnel (PT and PI) at minimum once a week to review subjects' training progress, performance, any complications, concerns or complaints that the subject expresses, and any changes in the health status of the subjects who had been seen over the course of the week. Senior personnel will re-assess and modify the training procedures as appropriate.

During the last week of training (week 12), the trainer will give subjects a survey to assess satisfaction with the training program to collect their feedback on factors such as tolerance, perceived strength, performance and health benefits, efficiency of training, choice to continue training, and if they would recommend this form of exercise to others.

The follow-up outcome assessment visit, which take place at our laboratory, will be conducted by the PhD student and overseen by the PI.

Visit 2 (midway visit)

Participants will come back to the lab 6-8 weeks from the beginning of the intervention. The follow-up visit intake form will be completed to identify any changes in the participants health or medical status, lifestyle or any other changes that could impact the participants ability to complete the exercise program. At this visit we will test their strength in the same way that it was tested on initial visit. Additionally, they will fill out the pain measure forms, the health and satisfaction form and the carpal tunnel questionnaire that were filled out at the first visit.

This visit is expected to take no more than 2 hours to complete.

Visit 3 (end of the exercise program)

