At the end of the 12-week intervention period, subjects will come back to the lab for the final visit. This visit will be scheduled 12-14 weeks after the start of the intervention. However, even if a participant is unable to come back at 12 weeks exactly, the exercise program will still end at 12 weeks.

The follow-up visit intake form will be completed to identify any changes in the participants health or medical status, lifestyle or any other changes that could impact the participants ability to complete the exercise program. At this visit subjects will complete all the measures that were completed during the first visit. This includes the pain measures, measure of health and function, carpal tunnel questionnaire, strength, power output and functional measures. These tasks are expected to take up to 5 hours to complete.

As stated above, three exercise sessions will be scheduled each week. We expect that this schedule will be modified due to scheduling conflicts, illness, etc. and it is possible that subjects may sometimes complete less than three visits per week. All visits that are changed or missed will be documented in the research record but will not be considered protocol deviations so long as they are completing a minimal number of sessions (10) per six-week period. If a subject completes less than 10 exercise sessions in a 6-week period they will be removed from the study.

As stated above, testing sessions at the HERL lab will be scheduled at 6 and 12 weeks from the baseline visit. We expect that this schedule will be modified due to scheduling conflicts, illness, etc. For this reason, subjects will be given a 2-week window (6-8, 12-14 weeks) in which to complete these visits. Testing sessions within this window will not be considered protocol deviations.

Eligibility Criteria

Inclusion Criteria:

- (1) have a neurological impairment secondary to a SCI or disease at T2 or lower
- (2) greater than 6 months post injury
- (3) use a manual wheelchair as primary means of mobility (at least 30 hrs. per week)
- (4) 18 to 65 years of age
- (5) provide signed medical release by primary care physician to engage in a high-intensity resistance training exercise program
- (6) live within 60 minutes driving time (1 hour) from the research center
- (7) able to perform a transfer independently to and from a wheelchair
- (8) have normal range of motion in the upper limbs.

Exclusion Criteria:

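### If Visit 1 runs in the order described, baseline strength follows exhaustive arm cranking and week-6 strength does not, which can inflate the week-6 primary change

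*Combined protocol and SAP*

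**What the plan says.** The primary outcome (Objective, Specific Aim 1) is the change in peak torque and grip from baseline to week 6 and to week 12. Peak and average power are compared between baseline and week 12 only.

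The Visit 1 text introduces the assessments with "If subjects successfully complete the vibration screening they will continue with the following assessments during Visit 1" and then gives the health survey, the power-output test, strength testing and functional testing, in that order. In the power-output test, "participants will be instructed to cycle as hard and as fast as they can for as long as they are able to". Repetition is set by "We will complete this process three separate times, with a minimum of 30 seconds of rest in between". An unloaded cool-down of the subject's own chosen length follows. No minimum time is set before strength testing.

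Muscle Strength Testing says "The torque measurements will be recorded in a randomized fashion for both arms for the following test maneuvers". It requires at least 60 seconds of rest between the practice and recorded trials, and "in between each muscle groups participants will rest a minimum of 2 minutes". It places strength before the functional tests.

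For week 6 (Visit 2) the text says "At this visit we will test their strength in the same way that it was tested on initial visit". The only other measures at that visit are an intake form and questionnaires. Visit 3 repeats all first-visit measures and lists them as ending in "carpal tunnel questionnaire, strength, power output and functional measures".

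The Statistical Plan specifies a repeated measures ANCOVA over the three time points. The only covariate it names is the number of training sessions completed, to be used if necessary.

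**The concern.** Arm cranking to exhaustion loads the same limbs whose torque is the primary outcome. If it precedes strength testing at baseline and is absent at week 6, the two measurements are made under different conditions, and the difference acts in the direction of the hypothesis. A subject who gained nothing from training could still show a gain at week 6.

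The analysis cannot separate this from training. It compares time points within subjects and has no term for group, test order or preceding activity. Nothing in the documents requires the sequence to be recorded, so the problem might not be recognisable afterwards.

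A second, smaller matter is the randomised manoeuvre order. The text does not say whether a subject keeps the order drawn at Visit 1. If it is redrawn, a muscle group tested early at one visit may be tested late at another.

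**Working it through.** **Inputs from the documents**

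| Visit | Arm ergometer | Strength | Order suggested by the text |
|---|---|---|---|
| 1 (baseline) | yes, 3 bouts | yes | ergometer described before strength |
| 2 (week 6) | no | yes | not applicable |
| 3 (week 12) | yes | yes | strength listed before power |

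The plan gives no expected gain, standard deviation, sample size or fatigue estimate, so there is no figure of its own to reproduce. The sizes below rest on assumed values.

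**Week 6.** Let f be the fraction of torque lost to residual fatigue at baseline, with none at week 6. If true strength is unchanged, the observed ratio of week 6 to baseline is 1/(1 − f), so the false gain is 1/(1 − f) − 1. With a true 10% gain, the observed gain is 1.10/(1 − f) − 1.

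| Assumed f | False gain | True 10% gain reads as |
|---|---|---|
| 0% | 0.0% | 10.0% |
| 2% | 2.0% | 12.2% |
| 5% | 5.3% | 15.8% |
| 10% | 11.1% | 22.2% |

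For scale only, the Background reports strength gains of 10% to 60% across earlier studies. Against the low end, a false gain of 2.0% is a fifth and 5.3% about half; 11.1% exceeds it.

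**Week 12.** If the ergometer comes first at both Visits 1 and 3, with the same f, the factor (1 − f) appears in both measurements and cancels from the relative change. If it comes first at Visit 1 and second at Visit 3, the false gain is the same as in the table. If the reverse, the ratio is (1 − f)/1, a false loss of f.

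**Redrawn manoeuvre order.** Suppose torque falls by L per position over K positions, and positions are drawn independently at each visit. The mean effect on change is 0, and its standard deviation for one subject and manoeuvre is L × √(2(K² − 1)/12).

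- K = 7 (six paired movements plus grip): √(2 × 48/12) = 2.83. For assumed L of 0.5%, 1% and 2%, the added SD is 1.4, 2.8 and 5.7 percentage points.
- K = 14 (both arms separately): √(2 × 195/12) = 5.70. The added SD is 2.9, 5.7 and 11.4 points.

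Simulation gave a mean near 0 and the same standard deviations. If one order is drawn per subject and kept, and the loss per position is constant, this term is 0.

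**The case against.** The strongest reply is that the protocol never says the ergometer comes first. That is correct: the order is inferred from the sequence of description. The one explicit link places strength before the functional tests and does not mention the ergometer. The overview in Study Design and Methods gives power no slot of its own. Power shares the baseline and week-12 schedule of functional testing, so it could be run there, after strength. A reader might infer that the plan mandates cranking before strength; it does not.

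The Visit 3 list is also weak evidence of a reversed order. It is an inventory, and it also places the health survey before the carpal tunnel questionnaire, whereas Visit 1 describes them the other way round. A reader might infer that the week-12 change is biased too. The documents do not support this, because both tests are done at both visits and no passage says that their order changes.

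Recovery is not wholly neglected. There is the cool-down, a practice trial, 60 seconds before recording and at least 2 minutes between muscle groups. Seven test types have six gaps, so at least 12 minutes of rest in all, and subjects may ask for more. Later manoeuvres may be little affected, so one value of f for every torque is probably too high, and f could be zero.

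It is also tempting to say that randomised order biases the change. It does not, and testing strength as at the first visit may already mean keeping the order.

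Nor can one say flatly that there is no control group. The training description at the end of the Visit 1 text refers to control and vibration groups, and the Background to vibration and non-vibration programmes. But the aims and the Statistical Plan compare no groups, so nothing planned would remove the effect.

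One part of the reply fails: that any consistent sequence would do. With the ergometer first at both Visits 1 and 3, week 6 would still be the only strength test without it. Only testing strength first, or an adequate fixed recovery, equalises all three visits.

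**Conclusion.** The point stands in conditional form and should be corrected. It is certain that the sequence is not fixed, that no minimum recovery separates cranking from strength testing, and that week 6 has no ergometer test. If a site follows the written order, and if some fatigue remains when torque is measured, the week-6 primary change is biased toward a gain. Its size cannot be taken from the documents; an assumed loss of 0% to 10% gives 0% to 11.1%. For week 12 there is a bias only if the order differs between Visits 1 and 3. Manoeuvre order is a matter of precision alone, and of secondary importance.

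**What to change.** - State one test sequence for all visits, in the Visit 1, Visit 2 and Visit 3 text: strength testing before the arm ergometer and the functional tests.
- Record at each visit the sequence actually used, so that departures can be examined.
- Draw each subject's manoeuvre and arm order once at Visit 1, store it and reuse it at Visits 2 and 3.

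This needs no new test or visit, only a reordering and one stored list per subject. The small downside is that the ergometer test then follows strength testing, but it does so equally at baseline and week 12, the only visits at which power is compared.

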After signing informed consent, all subjects will complete a basic information questionnaire. The questionnaire will survey the frequency of wheelchair usage, transfers, percentage of non-level transfers, basic demographics (age, gender, years since SCI, etc.), work history, history of medical problems, current medications, and alcohol and smoking usage.

Pain and Health Measures

Numerical rating scale (NRS): Subjects will complete this scale once for each upper limb joint (wrist, elbow, and shoulder). The subjects will be asked to rate their average, most severe, and least severe wrist, elbow or shoulder pain during the past 24 hours using an 11-point scale (i.e. 0-10) anchored at the ends by "no pain" and "worst pain ever experienced." An 11-point NRS measure of pain intensity allows for comparison across clinical trials of pain treatment and is recommended as a core outcome measure for chronic pain clinical trials. NRS pain measures are widely used and have been shown to be valid and reliable assessments of pain.

WUSPI – Wheelchair User's Shoulder Pain Index: The WUSPI is a 15-item, self-report instrument that measures shoulder pain intensity, within the last week, in wheelchair users during various functional activities of daily living, such as transfers, loading a wheelchair into a car, wheelchair mobility, dressing, bathing, overhead lifting, driving, performing household chores, and sleeping. The WUSPI is a valid and reliable measure of shoulder pain. This survey asses the previous tasks over the time span of the week leading up when the survey was being answered. Test-retest reliability of the total index score was 0.99 and Cronbach's alpha (internal consistency) was 0.98.

Carpal Tunnel Syndrome Self-Report Questionnaire: This self-report instrument includes two scales: a Symptom Severity Scale consisting of 11 questions and a Functional Status Scale evaluating 8 different activities. This instrument is reproducible, internally consistent, and responsive to clinical changes in symptoms.

Vibration Tolerance: Participants will be screened for their tolerance to the feeling of the vibration prior to collecting the biomechanics outcome measures. Participants will hold the dumbbell at 25Hz for 30 seconds with their arm at a forty-five-degree angle away from their bodies (position similar to a bicep curl). If they are unable to complete the assessment they will not be permitted to continue the study.

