Sessions will ideally be scheduled on a Monday, Wednesday and Friday to allow time for muscles to rest and rebuild in between training sessions. Prior to starting the weight training, subjects will go through a warm-up phase (approximately 5-10 minutes) and stretching phase (approximately 5 minutes). The warm-up phase will consist of non-resisted arm movements that parallel motions of the resistance exercises and forward and backward arms circles. The stretching phase will consist of stretching exercises for the arms, chest and upper back.

Subjects will perform nine training exercises. For each exercise, subjects will perform one repetition of each exercise at 60% of their 1 RM holding the high-frequency (40 Hz) vibrating dumbbell in a static arm posture. This posture will be at the point where the force generating output of the targeted muscle group is maximized. This point is at the 'End' range of motion (ROM) for each of the dynamic upper limb exercises with the exception of the biceps curl which occurs when the elbow is flexed at 90 degrees. Subjects will be asked to hold the 40 Hz vibrating dumbbell in the position for as long as they can until they reach a pain-free level of muscle exhaustion. The amount of time subjects hold on to the dumbbell will be recorded for each exercise and ideally will be 30-45 seconds, a standard isometric training goal for increasing muscle hypertrophy. Falling below or above this time will result in changes in the amount of dumbbell weight added or removed for the next session.

Two sets of each exercise will be performed alternating between the left and right sides. The resisted exercise phase is estimated to take about 40-50 minutes with total session time of 60-65 minutes. For the two exercises that require a supine position, the subject will transfer to a weight bench provided to them for the duration of the study and returned to HERL after the study ends. Subjects may choose to

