- (1) history of fractures or dislocations in the shoulder, elbow and wrist from which the subject has not fully recovered or joint replacement of any of the joints in the upper extremities
- (2) upper limb pain that interferes with the ability to propel or transfer
- (3) recent hospitalization for any reason (within the past three months)
- (4) pregnant women
- (5) history of coronary artery disease, coronary bypass surgery or other cardiorespiratory events

Statistical Plan

Distributions of all data will be examined. Should outliers or distributions that are nonlinear in nature be present, appropriate transformations will be performed. Means and standard deviations, or medians and ranges, as appropriate, will be calculated for all variables. A repeated measures ANCOVA will be used to examine primary (strength) and secondary outcome measures (pain, quality of life, power, transfer ability, propulsion characteristic) for the three time points. For significant models, post-hoc analyses with Bonferroni corrections will be used. Total number of training sessions completed will be entered as a covariate if necessary. The training progress (e.g. hold times) and training adaptations made and documented by the trainer during each session will be analyzed using graphical methods to further assess training effects that occur overtime.

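### The interval between the last training session and each follow-up test is not standardised, so strength and pain can be measured in different recovery states at Visits 2 and 3

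*Combined protocol and SAP*

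**What the plan says.** **Timing of tests.** For the midway visit: "Participants will come back to the lab 6-8 weeks from the beginning of the intervention". For the final visit: "This visit will be scheduled 12-14 weeks after the start of the intervention". The Visit 3 section then fixes the end of training regardless of the test date: "even if a participant is unable to come back at 12 weeks exactly, the exercise program will still end at 12 weeks". It also says that a test on any day inside either two-week window is not a protocol deviation.

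**Training schedule.** The training description under Visit 1 says: "Sessions will ideally be scheduled on a Monday, Wednesday and Friday to allow time for muscles to rest and rebuild in between training sessions". Each hold is taken to muscle exhaustion. Missed sessions are tolerated "so long as they are completing a minimal number of sessions (10) per six-week period", with no rule on where in the period they fall.

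**Outcomes.** Isokinetic strength is primary and is measured at both follow-up visits. Under Pain and Health Measures, the NRS asks for "average, most severe, and least severe wrist, elbow or shoulder pain during the past 24 hours", and the WUSPI looks back one week. Both are repeated at Visits 2 and 3. Muscle Strength Testing specifies rests within the visit (60 seconds and 2 minutes) but no recovery time since the last training session.

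**Analysis.** The Statistical Plan uses a repeated measures ANCOVA over three nominal time points. It adds: "For significant models, post-hoc analyses with Bonferroni corrections will be used". The only covariate it names is the total number of sessions completed, to be entered if necessary.

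**The concern.** The protocol recognises that muscles need recovery between sessions and controls rest between strength trials. It does not control recovery before the test session itself. Visit 2 falls inside the training period. Visit 3 can fall well after training has stopped. The two follow-up measurements can therefore differ in recovery state as well as in accumulated training.

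Recent exhausting sessions could depress strength or raise recalled pain at Visit 2. Idle time before a late Visit 3 could let strength recover or decline, and would move training out of the pain recall period. The planned analysis cannot separate these effects from the effect of training. Its hypotheses concern change over time, and although the training description still mentions a control group, the Statistical Plan names no between-group comparison that could cancel a visit-timing effect. Total sessions completed is no substitute: two participants with equal totals can differ by weeks in time since their last session.

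**Working it through.** The plan gives no figure for this interval, so there is nothing to reproduce. What follows is calendar arithmetic on its stated rules.

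**Inputs.** Sessions on Monday, Wednesday and Friday for 12 weeks (training description). Visit 2 window: weeks 6-8, days 42-56. Visit 3 window: weeks 12-14, days 84-98. Each window has 15 allowed days. Assumptions: day 0 is the first session and a Monday, and attendance is full.

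**Last session.** 12 × 3 = 36 sessions. The last is the Friday of week 12: 11 × 7 + 4 = day 81.

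**Gap = test day minus day of the last earlier session.**

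| | Visit 2 | Visit 3 |
|---|---|---|
| Shortest gap | 1 day (e.g. 43 − 42) | 84 − 81 = 3 days |
| Longest gap | 3 days (e.g. 42 − 39) | 98 − 81 = 17 days |
| Test days that follow a session day | 6 of 15 (43, 45, 47, 50, 52, 54) | 0 of 15 |
| Test days that are scheduled session days | 7 of 15 (42, 44, 46, 49, 51, 53, 56) | 0 of 15 |

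On the 7 session days, nothing says whether the session comes before or after the test, so the gap could be less than a day. On weekdays alone, the Visit 2 window has 11 days: 7 session days and 4 days after a session.

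**Pain recall.** On the 6 Visit 2 days that follow a session, the session lies close to or inside the 24-hour NRS period. This never happens at Visit 3. The WUSPI week always contains training at Visit 2. At Visit 3 the last session is more than 7 days earlier on days 89-98 (89 − 81 = 8), which is 10 of the 15 allowed days.

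**Sensitivity to the assumptions.**
- Wednesday or Friday start: Visit 2 stays at 1-3 days; Visit 3 becomes 2-16 days.
- Final training week missed (last session day 74): Visit 3 gap is 84 − 74 = 10 to 98 − 74 = 24 days.
- The 10-session minimum met early in the second six weeks (last session day 63): Visit 3 gap is 84 − 63 = 21 to 98 − 63 = 35 days.

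The pattern does not depend on the starting weekday, and 17 days is not the longest gap that the rules allow.

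**The case against.** The strongest reply is that the hypotheses compare weeks 6 and 12 with baseline, and that against baseline the plausible effects mostly work against the study. Residual fatigue or lost conditioning would lower measured strength, and soreness at week 6 would raise pain. This largely stands. A reader might infer that a pain reduction at week 12 could be produced simply by stopping training. The documents do not support that: baseline precedes all study training, so stopping returns a participant toward that state and cannot alone push pain below it. What remains is that a late Visit 3 can miss pain that training provoked, and that the post-hoc week 12 versus week 6 contrast compares unlike conditions.

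Three other cautions are fair.
- The soreness mechanism is not established here. Holds are meant to stay pain-free, training stops on pain, and the NRS asks about joints.
- Baseline cannot be called untrained and rested. Eligibility does not exclude prior resistance training, and in the listed order Visit 1 has three maximal arm-ergometer bouts before strength testing.
- A two-week window for conflicts and illness is ordinary, the study is exploratory, and a Visit 3 at week 12 may be only 2-3 days after the last session. How often late visits will occur is unknown.

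It is also true that the interval could be reconstructed, since each session is logged and missed visits are documented. But no use of it is planned, and logging does not standardise the measurement.

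**Conclusion.** The point holds as a gap in standardisation. Under the stated rules, with full attendance and a Monday start, the interval is 1-3 days at Visit 2 (possibly the same day) and 3-17 days at Visit 3, and longer if late sessions are missed. These are intervals that the plan permits, not intervals known to occur.

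The likely consequences are added noise, possible understatement of strength gains against baseline, possible masking of training-related pain at a late Visit 3, and a week 12 versus week 6 contrast that is hard to interpret. A reader might want to turn the idle fortnight into a percentage of the gain lost. The documents give no rate of loss, so neither the direction nor the size of any net bias can be calculated from them. This is a worthwhile, cheap improvement and does not by itself invalidate the baseline comparisons.

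**What to change.** 1. Hold the Visit 2 and Visit 3 tests at a stated minimum interval after the last session, the same for both. The protocol's own between-session spacing is one example, with testing before any session that day. This is workable: on all 7 scheduled session days in the Visit 2 window, the last earlier session is 2 or 3 days back.
2. Book Visit 3 in advance for the start of its window, keeping 14 weeks as the outer limit.
3. Derive days since the last session from the training log and report the distribution by visit.
4. Add a sensitivity analysis of strength and pain restricted to Visit 3 tests done early in the window, with the cut-off fixed before the data are examined. A pooled covariate for days since the last session is not a good substitute. It is undefined at baseline, and at 1-3 versus 3-17 days it nearly coincides with visit, so it could hardly separate recovery from the training effect.
5. Reconcile the time origin. The visit sections count from the start of the intervention, but later text in the Visit 3 section counts from the baseline visit.

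The cost is slightly less scheduling freedom and one derived variable. The restricted analysis will use fewer participants, and prompt attenders may differ from late ones, so it should be read as supportive.
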